### **Overall summary of subject incidence of treatment-emergent adverse events and**

by preferred term and worst severity grade will be provided by anti-AMG592 and [REDACTED] status. Subject incidence of events of interest (standardized MedDRA queries and/or Amgen Medical Queries) will also be summarized according to their categories, preferred term, and worst severity grade. Events of interest could include but are not limited to Hypersensitivity, Tachyarrhythmias, Tachypnea, Hematopoietic Cytopenia, **Eosinophilic Disorder**, Leucocyte Changes, Infection and Infestation, Cytokine Release Syndrome, **Drug Related Hepatic Disorder**, and Injection Site Reaction. Number of episodes and duration of treatment-emergent injection site reactions will be further summarized.

Subject incidence of treatment-emergent adverse events identified by COVID-19 standardized MedDRA queries and serious adverse events occurring on or after the COVID-19 infection will also be summarized.

Subject incidence of disease related events and fatal disease-related events will be tabulated by system organ class and preferred term. They are defined for this study in [Appendix D](#).

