The study will enroll subjects who are recipients of an allogeneic hematopoietic stem cell transplant (HSCT), have been diagnosed with moderate to severe steroid-refractory cGVHD per the 2014 cGVHD NIH Consensus Criteria, have received no more than 3 previous treatments for cGVHD (excluding topical agents), have a Karnofsky performance status score $\geq 50\%$, have adequate renal, cardiac and bone marrow function, have adequate hepatic and pulmonary function (unless related to cGVHD), and an estimated life expectancy of greater than 3 months. Subjects who are receiving systemic corticosteroids at baseline must be on a stable corticosteroid dose from 2 weeks prior to the first dose of efavaleukin alfa and must have an ongoing systemic prednisone requirement ≤ 1 mg/kg/day (or equivalent). Subjects who are receiving non-corticosteroid immunosuppressants at baseline must be on a stable dose from 2 weeks prior to the first dose of efavaleukin alfa. Subjects will be excluded from the study if they have active morphologic relapse/progression of hematologic malignancy post transplantation, received a donor lymphocyte infusion T-cell depleting, B-cell depleting or IL-2 signaling targeted medication within 12 weeks prior to starting efavaleukin alfa, received T regulatory cell expanding therapies, ibrutinib, imatinib, bortezomib, entospletinib, ruxolitinib or other JAK inhibitor, or an investigational drug or

device within 4 weeks prior to starting efavaleukin alfa, or have a known history of active tuberculosis.

For a full list of eligibility criteria, please refer to Section 6.1 to Section 6.2.

Treatments

Subjects will receive a SC dose of efavaleukin alfa QW or Q2W starting on day 1 until week 50 (Q2W dose) or 51 (QW dose). Subjects in phase 1b may continue to receive efavaleukin alfa at their current dosing regimen (QW or Q2W) for up to an additional **208 weeks** (through week **258** or week **259**, respectively) at the discretion of the Sponsor, following discussion and agreement between the principal investigator and medical monitor.

Efavaleukin alfa will be provided in glass vials.

Efavaleukin alfa will be stored between 2°C and 8°C. All doses will be fixed, and the qualified site personnel will prepare the appropriate dose for each subject.

Procedures

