## **3. Study Overview**

### **3.1 Study Design**

This is an open-label, multi-center phase 1b/2 study to evaluate the safety and efficacy of efavaleukin alfa in subjects with steroid refractory cGVHD.

The phase 1b part of the study will be conducted as a multiple ascending dose (MAD) study. Each dosing cohort will consist of between 3 and 6 DLT-evaluable subjects who will receive efavaleukin alfa SC either every week (QW) or every 2 weeks (Q2W) plus protocol permitted background therapy for 52 weeks. The DLT evaluation period is defined as 4 weeks after the first dose of study IP. At the discretion of the Sponsor, following discussion and agreement between the principal investigator and medical monitor, subjects responding to efavaleukin alfa (as assessed by the end of week 50), who wish to continue treatment, may continue to receive efavaleukin alfa treatment at their current dosing regimen for up to an additional 52 weeks. The remaining subjects will complete the week 52/EOT visit. All subjects who continue to receive efavaleukin alfa during the extended dosing period will be re-evaluated at week 76 for their response to treatment. Following discussion and agreement between the principal investigator and medical monitor, the Sponsor may decide to allow these subjects to continue treatment

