through week 102 (Q2W dose) or week 103 (QW dose). Subjects participating in extended dosing will complete the week 104/end of extended treatment (EOET) visit. At the discretion of the Sponsor, following discussion and agreement between the principal investigator and medical monitor, subjects responding to efavaleukin alfa (as assessed by the end of week 104), who wish to continue treatment beyond week 104, may continue to receive efavaleukin alfa treatment at their current dosing regimen for up to an additional 156 weeks. Only subjects who are deemed eligible to continue extended dosing beyond week 102 or week 103 will complete dosing at week 104. The remaining subjects will complete the week 104/EOET visit. All subjects who continue to receive efavaleukin alfa during the extended dosing period will be re-evaluated every 6 months for their response to treatment. Following discussion and agreement between the principal investigator and medical monitor, the Sponsor may decide to allow these subjects to continue treatment through week 258 (Q2W dose) or week 259 (QW dose). Subjects participating in extended dosing through week 258 or 259 will complete the week 260/EOET visit. All subjects will complete the 6-week safety follow-up after the last dose of efavaleukin alfa.

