### **Number of days on IP**

Number of days on IP is defined as last dose date – first dose date + 1

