## **9. Statistical Methods of Analysis**

### **9.1 General Considerations**

Standard descriptive statistics will be provided. All binary endpoints will be summarized using the number and percentage of subjects. All continuous endpoints will be summarized using descriptive statistics including mean, standard deviation, minimum, maximum, and number of non-missing observations (n). Summaries will be provided at all scheduled time-points unless specified otherwise. Data collected at unscheduled visits or time-points will be included in the analysis unless stated otherwise. **All safety and efficacy analyses will be performed using the Safety Analysis Set based on subject's actual treatment received.**

Only critical subject-level data listings will be provided in the clinical study report.

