#### **9.6.8            Exposure to Investigational Product**

The number of days on IP and the total dose of IP will be summarized using descriptive statistics. Number and percentage of subjects who missed IP doses due to COVID-19 measures will be summarized. The final IPD list will be used to identify such subjects.

A listing of the unique manufacturing lot numbers, and a listing of the subjects administered each manufacturing lot number will be provided

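### SAP 9.6.2 counts injection site reaction episodes with no denominator or time limit, and no injection count is planned, although weekly cohorts are scheduled for twice the injections

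*SAP*

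**What the plan says.** SAP 9.6.2 plans two displays of ISRs. The first treats them as an event of interest: "Subject incidence of events of interest (standardized MedDRA queries and/or Amgen Medical Queries) will also be summarized according to their categories", and also by preferred term and worst grade. The second is a count of repeat events: "Number of episodes and duration of treatment-emergent injection site reactions will be further summarized". The SAP does not say whether episodes are expressed per subject, per injection or as a cohort total. It sets no time limit beyond the general treatment-emergent window.

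Grouping follows SAP 9.1: "All safety and efficacy analyses will be performed using the Safety Analysis Set based on subject's actual treatment received". The groups differ in schedule. SAP 3.1 describes subjects "who will receive efavaleukin alfa SC either every week (QW) or every 2 weeks (Q2W) plus protocol permitted background therapy for 52 weeks"; cohorts 1a, 3 and 5 are Q2W, and cohorts 2a and 4 are QW. The protocol synopsis (Treatments) has dosing "starting on day 1 until week 50 (Q2W dose) or 51 (QW dose"). Subjects judged to be responding may be allowed to "continue treatment through week 258 (Q2W dose) or week 259 (QW dose").

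On exposure, SAP 9.6.8 states: "The number of days on IP and the total dose of IP will be summarized using descriptive statistics". In SAP 5.4, "Number of days on IP is defined as last dose date" minus first dose date plus one, so it is a calendar span. Neither quantity is a number of injections.

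**The concern.** Each injection is a fresh opportunity for a local reaction, so an episode count rises with the number of injections even when the drug is no more irritating per injection. The other adverse event tables in SAP 9.6.2 count each subject once. The ISR episode summary is the one that counts repeats, and so the one most sensitive to injection number.

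The cohorts differ in schedule by design and in follow-up by circumstance, through early stopping and extension for responders only. A reader comparing episode counts across cohorts could not tell a difference in local reactogenicity from a difference in injections given. The event is not rare: Protocol 3.2.3 places mild injection-site erythema among the most common adverse events. If reactions are common, subject incidence approaches 100% in every cohort, and the episode count becomes the display that readers rely on.

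**Working it through.** **The plan's own figure.** The only safety probability stated nearby is the chance of seeing at least one event of 5% incidence (Protocol 10.1.1, SAP 3.2). 1 − 0.95^40 = 0.8715 and 1 − 0.95^30 = 0.7854, which agree with the stated 87% and 79%. The documents give no ISR rate and no injection count.

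**Scheduled injections.** QW is day 1 plus every week to the last dosing week. Q2W is day 1 plus every second week.

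- Main period: QW 1 + 51 = 52; Q2W 1 + 25 = 26; ratio 2.0.
- To weeks 103/102: 104 v 52; ratio 2.0.
- To weeks 259/258: 260 v 130; ratio 2.0.

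**Episodes and incidence at equal treatment time.** Let p be the risk of an ISR per injection, assumed constant and equal in both schedules. The value of p is an assumption, shown over a range. With m injections, expected episodes are m·p, and the probability of at least one ISR is 1 − (1 − p)^m. Over the main period (m = 52 and 26):

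| p | Episodes QW | Episodes Q2W | Incidence QW | Incidence Q2W | Incidence ratio |
|---|---|---|---|---|---|
| 0.005 | 0.26 | 0.13 | 0.229 | 0.122 | 1.88 |
| 0.01 | 0.52 | 0.26 | 0.407 | 0.230 | 1.77 |
| 0.02 | 1.04 | 0.52 | 0.650 | 0.409 | 1.59 |
| 0.05 | 2.6 | 1.3 | 0.931 | 0.736 | 1.26 |
| 0.10 | 5.2 | 2.6 | 0.996 | 0.935 | 1.06 |
| 0.20 | 10.4 | 5.2 | 1.000 | 0.997 | 1.00 |
| 0.30 | 15.6 | 7.8 | 1.000 | 1.000 | 1.00 |

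The episode ratio is 2.0 in every row. The incidence ratio lies between 1 and 2 and falls towards 1 as reactions become common.

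**Unequal treatment time.** At equal p the episode ratio equals the injection ratio:

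- QW 52 weeks v Q2W 104 weeks: 52/52 = 1.0.
- QW 40 v Q2W 52: 40/26 = 1.54.
- QW 52 v Q2W 40: 52/20 = 2.6.
- QW 104 v Q2W 52: 104/26 = 4.0.

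These are examples, not bounds.

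**Chance variation.** In 10,000 simulated comparisons of 6 v 6 subjects at p = 0.05 and full main-period dosing, the episode ratio had median 2.0 and 95% range 0.87 to 5.67. Per injection, the median was 1.0 (0.43 to 2.83). Injections were simulated as independent; positive within-subject correlation would widen both ranges.

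**Do the planned exposure tables show the difference?** Doses are redacted, but Protocol Table 3-1 gives predicted exposure per dosing interval. Assume its rows follow cohort order, which the Q2W/QW sequence fits. Cohorts 1a (Q2W) and 2a (QW) then match over two weeks: AUC 549 v 2 × 274 = 548 hr·ng/mL. Protocol 5.4 calls exposure roughly dose proportional, so total dose and days on IP would look alike in these two cohorts while injections differ twofold. Cohorts 1a (Q2W) and 4 (QW) have similar predicted exposure per dose (AUC 549 v 553; Cmax 18.9 v 20.3 ng/mL). Equal risk per injection is therefore not a far-fetched case, although systemic exposure is only a proxy for local reaction.

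**After the change.** At p = 0.05 over 52 weeks, 2.6 v 1.3 episodes per subject become 5.0 v 5.0 per 100 injections.

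**The case against.** The strongest reply is that little depends on this table. SAP 1 and 3.1 report early termination, with the expansion cohort and phase 2 cancelled. SAP 10 drops the phase 1b interim analysis, and SAP 2.2 has no statistical hypothesis. Dose level reviews used subject-level listings and plots, with the Bayesian model if required (SAP 7.1). This stands: no in-study dose choice or error rate is shown to depend on ISR episode counts.

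A reader might infer that QW cohorts will look twice as reactogenic in the report. The documents do not support that. The SAP leaves the unit of the episode summary open, so a per-subject count is only an inference. Doubling also requires equal treatment time and constant, equal risk. The planned incidence table would show little or no QW excess if reactions are common.

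Raw counts are also a legitimate measure of burden, since a weekly regimen does expose the subject to more injections. That stands too, and the counts should stay. They simply cannot be read as risk per injection.

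Finally, a reader could divide total dose by the fixed dose to recover injections. This works on average where the dose never changed. It fails for cohort 5 subjects whose dose was reduced (SAP 3.1), and it cannot isolate the first 52 weeks.

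**Conclusion.** The point holds as a minor reporting gap. The episode summary has no stated denominator or time limit, injections are not summarised, and scheduled injections differ exactly 2:1. At equal treatment time and an assumed equal, constant risk per injection, expected QW counts are twice Q2W counts. Unequal treatment time gave ratios from 1 to 4 in the cases worked. Whether risk per injection really is equal cannot be judged, because the doses are redacted and no ISR rate is given. The consequence is limited to how local tolerability is compared across cohorts in the study report.

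**What to change.** In SAP 9.6.8, add the number of injections received, by cohort. In SAP 9.6.2, add ISR episodes per 100 injections by cohort, both over all treatment and restricted to week 52. The restriction matters because only responders extend; SAP 9.6.9 already limits its corticosteroid-reduction summary in this way. State the unit of the raw episode count, and keep it and the subject-incidence table.

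No new data are needed. The CRF records administrations (Protocol Table 7-1), SAP 5.4 already derives dose administered from them, and event onset dates are collected (Protocol Appendix 4). The cost is a few table rows.

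There is a small downside. A pooled rate is weighted towards subjects with long exposure (up to 260 injections against 52) and ignores clustering within subjects, in cohorts of about 6. Show it beside the per-subject counts and make no inferential claim from it.

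Do not add the proportion of injections followed by an ISR unless an attribution window is defined first. The event attributes listed in Protocol Appendix 4 do not link an event to a particular dose.

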#### 9.6.2.1 Dose Limiting Toxicities

The analysis of the probability of DLT will be based on the Dose Escalation part of the study defined in Section [3.1](#). A listing and summary of the subject incidence of DLT will be provided should they occur. After there is at least 1 DLT observed at any dose level, a Bayesian logistic regression model (BLRM) ([Bailey et al, 2009](#); [Neuenschwander et al, 2008](#)) will be used to inform dose escalation and the results of this analysis will be provided to the each DLRM. Three toxicity probability intervals (TPI) of DLT will be defined: target TPI (20% to 30%), excessive TPI (30% to 60%) and unacceptable TPI (60% to 100%). Adverse events meeting DLT criteria after week 4 and PD information may also be included in the model, as available. The model will recommend an MTD as the dose with highest probability in the target TPI, but with less than 25% probability in excessive TPI or unacceptable TPI. Lower dose levels, intermediate dose levels, or alternative dosing schedules may be considered based on all available information as long as they do not exceed the estimated MTD per the model.

Let  $\mathbf{d} = (d_1, \dots, d_k)$  denote the vector of all efavaleukin alfa doses to be studied in the study. The probability of a DLT at dose level  $d_i, i=1, \dots, k$  is assumed to follow a Bernoulli distribution with probability  $p_i$  where the logit of  $p_i$  increases linearly with the log of the standardized dose in the following 2-parameter logistic model:

$$\log \left[ \frac{p_i}{1 - p_i} \right] = \text{logit}(p_i) = \log[a] + \exp(\log[b]) \log\left(\frac{d_i}{\max(\mathbf{d})}\right)$$

where a and b are random variables and  $d_i$  is dose level represented by predicted

[REDACTED]  $d_k$  is an additional dose assuming Treg concentration = [REDACTED] that's higher than the currently planned doses. Thus  $\mathbf{d} = [REDACTED]$ . If additional dose cohorts were added during study conduct (e.g., decision following a DLRM), the value of  $\mathbf{d}$  will be updated.

The probability of each TPI and of a DLT will be summarized by dose along with the estimated dose-toxicity curve. A final estimate of the MTD will be estimated from the Bayesian model by utilizing all DLT-evaluable subjects. Please refer to [Appendix C](#) for more details on the BLRM and its operation characteristics. Before each DLRM, the above BLRM will be fitted with the prior distribution as specified in [Appendix C](#). This model will only be used to aid DLRM dosing decision thus the recommendation of the model is non-binding in nature.

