## **2. Objectives, Endpoints and Hypotheses**

### **2.1 Objectives and Endpoints**

Objectives	Endpoints
Primary	

• To evaluate the safety and tolerability of multiple ascending doses of efavaleukin alfa in subjects with steroid refractory chronic graft versus host disease (cGVHD)

	

• Incidence of dose limiting toxicities (DLTs) at first 4 weeks

• Incidence of all treatment-related and treatment-emergent adverse events and serious adverse events

Secondary	
Exploratory	

Objectives	Endpoints

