Five dose levels are planned: [REDACTED] µg every 2 weeks (Q2W) (cohorts 1a), [REDACTED] µg every week (QW) (cohorts 2a), [REDACTED] µg Q2W (cohort 3), [REDACTED] µg QW (cohort 4), and [REDACTED] µg Q2W (cohort 5). Dose levels 1a ([REDACTED] µg Q2W) and 2a ([REDACTED] µg QW) will be enrolled concurrently. Three subjects each will be assigned to cohorts 1a ([REDACTED] µg Q2W) and 2a ([REDACTED] µg QW) alternately (total of 6 subjects). After the last subject completes the DLT evaluation period, a dose level review meeting (DLRM) will occur and if deemed necessary, 3 additional subjects each will be assigned to cohorts 1a and 2a alternately (total of 6 subjects) to gain additional information. After the last subject completes the DLT evaluation period, a DLRM will occur and if dose escalation is deemed appropriate, subjects will be enrolled in cohorts 3 ([REDACTED] µg Q2W) 4 ([REDACTED] µg QW), and 5 ([REDACTED] µg Q2W) as follows: first, 3 subjects will be enrolled in cohorts 3. An internal safety review will be conducted by the Amgen Medical Monitor and Global Safety Officer after the first 3 subjects complete the DLT evaluation period. If concerning safety issues are identified, a DLRM will occur to assess if it is safe to proceed with additional enrollment in cohort 3 and concurrent enrollment in cohort 4. If no concerning safety issues are identified in these first 3 subjects, enrollment of the remaining 3 subjects in cohort 3 will proceed without a DLRM. Concurrently, enrollment of 6 subjects in cohort 4 will begin with alternate assignment of subjects between cohorts 3 and 4 until enrollment of cohort 3

has completed. Enrollment of 6 subjects in cohort 5 will begin after the DLRM for cohort 4 is complete. DLRMs for cohorts 3, 4 and 5 will occur after the last subject in that cohort completes the DLT evaluation period.

[figure not shown]
All planned dose levels for a given cohort may be adjusted at any time based on emerging data. Additional dosing cohorts may be added, removed or substituted at any time based on emerging data and the results of continuous modeling. **As a result of a recommendation from an ad hoc DLRM, Amgen discontinued enrollment to cohort 5 at the planned [REDACTED] mcg Q2W dose. Subjects who were on-going at the time of this decision had their dose reduced to [REDACTED] µg Q2W for their remaining visits.**

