## **Actual Treatment Received**

---

**Actual treatment received is the IP the subject actually received regardless of the dose specified in the protocol for the cohort. In cases where a subject received multiple different efavaleukin alfa doses, the actual treatment received will be based on the highest efavaleukin alfa dose received.**

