### **Dose Reduction Period**

**For cohort 5 subjects, the time period from the first dose of IP at the reduced dose (█ mcg) until end of study, if applicable.**

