### **Dose Limiting Toxicity (DLT)**

The DLT evaluation period for each subject is 4 weeks from the first dose of efavaleukin alfa. To be evaluable for a DLT, subjects must have received at least 2 doses of efavaleukin alfa, or have experienced a DLT within the DLT evaluation period. All subjects who experience a DLT will discontinue study therapy and complete safety follow up. Dose limiting toxicity events will be used to guide dose escalation decisions and to determine the maximum tolerated dose as described in Section [3.1](#).

These events will be marked as DLT on Events eCRF.

[figure not shown]
The following DLT criteria apply to the study:

[figure not shown]
- Non-hematological toxicity  $\geq$  grade 4 related to efavaleukin alfa. Non-hematological laboratory abnormalities without clinical significance will not be considered DLTs (based upon the investigator's discretion in conjunction with Amgen).
- Hematological toxicity  $\geq$  grade 4 related to efavaleukin alfa defined as decrease in peripheral counts (ANC or platelets) persisting longer than 72 hours, as measured by 2 separate results, that are not related to malignant disease relapse, infection, or other etiologies.
- Constitutional events (i.e., fever, fatigue)  $\geq$  grade 3 that are classified as serious adverse events by the investigator and related to efavaleukin alfa.
- Infection: Infection is considered an expected complication of cGVHD and its treatment. cGVHD itself increases the risk of infection, including life threatening infection. Therefore only grade 4 or 5 infections considered by the investigator to be related to efavaleukin alfa will be reviewed by the DLRM to determine whether the infection is considered a DLT.

[figure not shown]
Subjects who develop an uncontrolled grade 4 life threatening infection (e.g., sepsis, ARDS), as assessed by the investigator, will discontinue efavaleukin alfa and remain in the study for safety follow-up (see Section 5.4) after completing the 4-week DLT evaluation period, subjects will be evaluated by standard safety reporting.

[figure not shown]
2014 cGVHD NIH response Consensus criteria algorithm (NIH Form A - 2014)

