### Appendix C. Bayesian Logistic Regression Model

[figure not shown]
The study will use BLRM to guide dose escalation. The MTD target toxicity probability interval for DLT is (0.20, 0.30), and TPIs of (0.30, 0.60) and (0.60, 1.00) are defined as excessive and unacceptable, respectively. The design seeks to identify a dose most likely to have a DLT rate in the target TPI, but with overdose control that limits the possibility the dose has an excessive or unacceptable DLT rate (Babb et al, 1998).

Let  $\mathbf{d}=(d_1, \dots, d_k)$  denote the vector of all efavaleukin alfa doses to be studied in the study. The probability of a DLT at dose level  $d_i, i=1, \dots, k$  is assumed to follow a Bernoulli distribution with probability  $p_i$  where the logit of  $p_i$  increases linearly with the log of the standardized dose in the following 2-parameter logistic model:

$$\log\left[\frac{p_i}{1-p_i}\right] = \text{logit}(p_i) = \log[a] + \exp(\log[b]) \log\left(\frac{d_i}{\max(\mathbf{d})}\right)$$

where a and b are random variables and  $d_i$  is dose level represented by predicted

[REDACTED]).  $d_k$  is an additional dose assuming Treg concentration = [REDACTED] that's higher than the currently planned doses. Thus  $\mathbf{d} = [REDACTED]$ . If additional dose cohorts were added during study conduct (e.g., decision following a DLRM), the value of  $\mathbf{d}$  will be updated.

A minimally informative prior distribution (Neuenschwander et al, 2008) was selected for  $\theta = (\log[a], \log[b])$ , where the probability that the true DLT rate is  $\leq 0.20$  at the lowest dose is 0.90 and the probability the true DLT rate is  $\leq 0.50$  at the maximum dose is 0.90. Median values for  $p_i$  were interpolated per the logistic model. For each  $d_i$ , 2 quantiles for  $p_i$  were selected from a minimum informative Beta distribution with the target median. This set of quantiles fully specified a target prior for theta. A bivariate normal distribution for  $\theta$  was assumed where  $(\log[a])$  has a normal distribution with mean ma and standard deviation sa, and  $(\log[b])$  has a normal distribution with mean mb and standard deviation

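### Should DLT-criteria events after week 4 be kept out of the model that gives the final MTD?

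*SAP*

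**What the plan says.** The endpoint in SAP 2.1 is "Incidence of dose limiting toxicities (DLTs) at first 4 weeks". The DLT set in SAP 6.2 uses the same window and requires at least two doses or a DLT. Under the DLT definition in SAP 5.5, "after completing the 4-week DLT evaluation period, subjects will be evaluated by standard safety reporting". SAP 9.6.2.1, SAP 3.1 and Protocol 5.1.1 all then add: "Adverse events meeting DLT criteria after week 4 and PD information may also be included in the model, as available".

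The model in Appendix C has no time or exposure term: a DLT at a given dose "is assumed to follow a Bernoulli distribution with probability" depending on dose alone. Section 9.6.2.1 adds that "A final estimate of the MTD will be estimated from the Bayesian model by utilizing all DLT-evaluable subjects", without naming the event window, and calls the model's recommendation non-binding.

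On dose, SAP 3.1 reports that enrolment to cohort 5 stopped at its planned dose. "Subjects who were on-going at the time of this decision had their dose reduced to" a lower level. Under SAP 5.1, for a subject who received several doses, "the actual treatment received will be based on the highest efavaleukin alfa dose received", and SAP 9.1 applies that rule to all safety analyses. SAP 5.3 defines a Dose Reduction Period for cohort 5 as "the time period from the first dose of IP at the reduced dose" until end of study, but 9.6.2.1 does not use it.

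**The concern.** A 4-week rate and a rate that counts later events are different quantities, yet both would be judged against the same 20% to 30% target interval. If the hazard were constant, a 4-week rate of only 1.7% to 2.7% would reach that interval by week 52: 1 − 0.983^13 = 0.20 and 1 − 0.973^13 = 0.30. Cohorts 1a and 2a enrolled first and are generally followed longest, so late events would tend to collect at the lower doses and flatten the dose-toxicity curve. The simulations described in Appendix C mention no late events.

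The study is open label and the wording is permissive, so inclusion could be decided once the events are known. The highest-dose rule could also charge an event after the cohort 5 dose reduction to the higher dose. At stake is the reported final MTD.

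A smaller worry is that two doses are a full 4-week course on Q2W (days 1 and 15) but half of one on QW (days 1, 8, 15 and 22).

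**Working it through.** **Inputs from the plan.** Appendix C gives logit(p) = log a + b·log(d/max d). The pair (log a, log b) is bivariate normal with means −1.283 and 0.280, standard deviations 1.002 and 0.770, and correlation −0.568. A dose is admissible if P(p ≥ 0.30) is below 0.25. Among admissible doses, the one with the highest probability in 20% to 30% is recommended.

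**Plan's own figure.** At the maximum dose the log term is zero, so P(p ≤ 0.50) = P(log a ≤ 0) = Φ(1.283/1.002) = 0.8998. The SAP states 0.90, so the prior is reproduced.

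**Assumptions.** Doses are redacted. Four d/max grids were tried for cohorts 1a, 2a, 3, 4 and 5:
- G1: 0.15, 0.2, 0.3, 0.4, 0.6
- G2: 0.1, 0.2, 0.3, 0.4, 0.67
- G3: 0.25, 0.35, 0.45, 0.55, 0.75
- G4: 0.25, 0.25, 0.5, 0.5, 0.75

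The SAP's other prior statement, P(p ≤ 0.20) = 0.90 at the lowest dose, implies a lowest d/max of about 0.12, so G1 and G2 fit better. The posterior is prior × Π p^y (1 − p)^(n − y), evaluated on a 601 × 601 grid.

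**Final estimate.** P(p ≥ 0.30) at cohort 5, with six evaluable subjects per cohort and late events placed one per cohort from 1a upward:

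| Data | G1 | G2 | G3 | G4 |
|---|---|---|---|---|
| Cohort 5 at 1/6, others 0/6 | 0.002 | 0.005 | 0.002 | 0.003 |
| plus 1 late event | 0.015 | 0.028 | 0.014 | 0.017 |
| plus 2 | 0.048 | 0.076 | 0.042 | 0.049 |
| plus 3 | 0.113 | 0.161 | 0.098 | 0.112 |
| plus 4 | 0.217 | 0.285 | 0.192 | 0.214 |
| Cohort 5 at 2/6, others 0/6 | 0.012 | 0.024 | 0.012 | 0.015 |
| plus 3 | 0.219 | 0.289 | 0.194 | 0.217 |
| plus 4 | 0.358 | 0.442 | 0.325 | 0.353 |

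With 1/6 in cohort 5, four late events cross 0.25 on one grid. With 2/6, three cross on one grid and four on all of them.

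**During escalation.** Take cohorts 1a, 2a and 3 at 0/6, 0/6 and 1/6. One late event in 1a moves cohort 5 from 0.058, 0.099, 0.054, 0.058 to 0.185, 0.262, 0.165, 0.179, so G2 crosses. That picture leaves cohort 4 empty, whereas SAP 3.1 normally enrols cohort 4 alongside the last three subjects of cohort 3. Adding three DLT-free cohort 4 subjects gives 0.115, 0.174, 0.100, 0.114, and no grid crosses.

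**A second dose scale.** Six geometric levels were used, with the second and third equal as their DLT probabilities are in SAP Table 2. The first four levels had six subjects each, with one 4-week DLT at the fourth. For lowest-to-highest ratios 0.1, 0.2, 0.3 and 0.4, one late event at the lowest level moves the top level from 0.27, 0.17, 0.11, 0.07 to 0.41, 0.29, 0.20, 0.14. At ratio 0.2 the recommendation drops from the top level to the one below. That top level is d/max = 1, which Appendix C assigns to an extra dose above those planned. The level below it reaches at most 0.104.

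**Dose attribution.** One event after dose reduction charged to cohort 5 (1/6 becoming 2/6) gives 0.002-0.005 becoming 0.012-0.024.

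**Half-dosed QW subjects.** Dropping two DLT-free subjects from each of cohorts 2a and 4 gives 0.002-0.005 becoming 0.004-0.008.

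**How many late events?** Neither document gives a rate. Let p be the 4-week rate and f the ratio of later to early hazard. Weeks 5 to 52 are twelve 4-week blocks, so 24 subjects are expected to have 24·(1 − p)·(1 − (1 − p)^(12f)) late events. This is 0.56 for p = 0.02, f = 0.1 and 6.04 for p = 0.05, f = 0.5.

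**The case for a change.** The strongest case for a change is that two analysts following this SAP could report different MTDs. The sentences at issue are not redacted, so hidden text does not explain the gap, and a few lines would close it. At the upper end of the assumed hazards, four or more late events among 24 subjects is not remote. The omission is real: no trigger, time limit or follow-up adjustment is tied to the model, and the highest-dose rule is written for the Safety Analysis Set without being linked expressly to the DLT set.

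Other parts do not stand. Dose attribution is not absent, because SAP 5.1 with 9.1 supplies a rule. Protocol 7.4.2.1.1 bars individual dose changes before a later dose is fixed, so in practice the question concerns only dose-reduced cohort 5 subjects. Who judges a late event is largely settled by the DLT criteria themselves: the investigator for relatedness, the investigator with the sponsor for laboratory abnormalities, and the DLRM for infections. Under Protocol Appendix 3, the DLRM reviews data from after the DLT period anyway.

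Restricting the main MTD to 4-week events also has a cost. Each added event raised the estimated toxicity in these runs, so leaving such events out gives a less cautious MTD for a treatment planned for 52 weeks or longer. If late events were frequent enough to move the estimate, that would itself be worth knowing.

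**Conclusion.** No change follows. The text leaves a permissive option without detail, and the analysts can settle it sensibly by saying which events entered the reported fit. Admitting late toxicity is a deliberate choice made in both documents, and it errs towards caution.

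Little depends on the result. The model is run only after a DLT, and neither document reports one. SAP 2.1 no longer ties the primary objective to estimating the MTD, as Protocol 4.1 did. No further dosing stage is planned, and the 4-week primary incidence is untouched.

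In the final-estimate runs, one late event leaves the recommended planned level unchanged (at most 0.028 with 1/6 in cohort 5). A shift on all four grids needs four late events plus 2/6 in cohort 5. The half-dosing effect reaches at most 0.008 and is immaterial.

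These sizes rest on assumed dose grids, assumed event counts and six evaluable subjects in cohort 5. The last is not established, because enrolment there was stopped. The true effect therefore cannot be sized from the documents.
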